ASCO Survey on COVID-19 in Oncology (ASCO) Registry

Study Schema - 10.6.2020

Rationale

The COVID-19 Pandemic presents a unique opportunity to capture information on how a disease outbreak affects delivery of high-quality cancer care. ASCO is providing the means for the oncology community to rapidly submit data that will inform both current cancer care and provide information to help guide decision-making for future disease outbreaks. While other entities have launched COVID-19 cancer registries, ASCO has extensive relationships with the entire cancer care community, particularly private practices that may be caring for the majority of cancer patients with COVID-19. ASCO's registry collects information about patients undergoing treatment for cancer and with confirmed COVID-19 infection based on a positive test. Unlike other registries, ASCO's registry collects follow-up information on both COVID-19 disease and cancer outcomes at 30-day intervals for the first 90 days and 90-day intervals thereafter up to one year after COVID-19 diagnosis.

Project Objectives:

Capture and describe cancer and COVID-19 status at COVID-19 diagnosis, and cancer and COVID-19 outcomes of patients with cancer and COVID-19 from participating cancer practices/institutions. Data collected will include treatment approaches, cancer status, changes to cancer treatment plans in patients with confirmed SARS-CoV-2 infection, status of COVID-19 infection (e.g., severity of symptoms, need for ventilator, hospitalization, etc.) and cancer (e.g., cancer progression, treatment-related changes/modifications, etc.).

Project Deliverables:

- Periodic Reports on Patient Population, Estimates of Disease Severity, Treatment Modifications, and Clinical Outcomes Among Patients – for participating sites and publicly accessible on ASCO websites for the oncology community
- Manuscript(s) for Submission to Peer-Reviewed Journals

Research Objectives:

Objective 1: Describe the distribution of symptoms and severity of COVID-19 among patients with cancer (on active treatment or on adjuvant treatment within 12 months after surgical resection) who have confirmed infection of SARS-CoV-2

- **Objective 1.1:** Describe distribution of symptoms and severity of COVID-19 stratified according to demographic characteristics, including age, cancer type, cancer extent, race, ethnicity, geography, type of therapy received, smoking status, comorbidities, etc.
- **Objective 1.2:** Identify characteristics independently associated with severity of COVID-19 in cancer patients.

Objective 2: Examine SARS-CoV-2 viral infection outcomes (ongoing, recovery, hospitalized, not in ICU; hospitalized in ICU; placed on ventilator; death due to COVID-19 disease complications) and

cancer outcomes (stable, response to treatment, progression, delayed treatment, treatment discontinued, and death)

- Objective 2.1: Stratify patients with SARS-CoV-2 viral infection according to characteristics
 described in Objective 1.1 to examine whether any of the characteristics are independently
 associated with COVID-19 and/or cancer outcomes
- Objective 2.2: Examine the relationship between SARS-CoV-2 viral infection outcomes and cancer outcomes and whether SARS-CoV-2 viral infection outcomes are independently associated with cancer outcomes

Objective 3: To describe effects of the COVID-19 pandemic on cancer practices in the U.S., including changes in staffing and resource availability, prioritizations for patient care, and modification of interactions between care providers and patients (including use of telemedicine)

Eligibility Criteria:

The registry will collect data about patients with a cancer diagnosis who have a confirmed SARS-CoV-2 infection and are being treated at participating cancer practices/institutions within the United States.

Patients in one of the four categories are eligible:

- 1. Patients with a new cancer diagnosis and in the process of cancer staging and/or receipt of initial cancer therapy
- 2. Patients with clinically evident cancer receiving anti-cancer treatment,
- 3. Patients who are disease free, but receiving any type of adjuvant therapy within 1 year following surgical resection (including hormonal treatments), and
- 4. Patients with clinically evident cancer receiving supportive care only.

Statistical Considerations and Reporting

ASCO's Center for Research and Analytics (CENTRA) will periodically create reports to share with participating practices and the general cancer community, and submit manuscripts for publication. Reports will summarize overall and stratified by patient characteristics, such as disease sites and stage, age and comorbidities. Reports or publications will also include cancer treatment delay and discontinuation of cancer treatments including surgery, radiation and drug-based therapies, due to the patient's COVID-19 disease and to other factors, with stratification by other variables as described above. Changes in practices' patterns of care, staffing, resources, and interactions with patients will also be evaluated and summarized.

As there is no hypothesis testing planned, there is no required sample size and providing repeated reports, with cumulative information, will not affect validity of results. Confidence intervals will be provided where appropriate to demonstrate precision of estimates.

IRB Review

ASCO received approval from the Western Institutional Review Board (WIRB):

"We determined this study is exempt from IRB review because it does not meet the definition of human subject as defined in 45 CFR 46.102. Specifically this study will [sic] deidentified data in the form of limited data sets from the participating clinics and institutions and you will enter into Data Use Agreements, and you will not otherwise interact with the patients."

The WIRB letter is available on the ASCO Registry website. ASCO encourages practices to rely on the WIRB review. If local IRB approval is necessary, the review must be completed before the practice can execute the data use agreement (DUA) with ASCO.

Practice Expectations (Refer also to study calendar in Appendix.)

- Review study schema, data collection elements, and WIRB determination.
- Complete practice contact information (link available at the ASCO Registry website) and download the DUA. In the interest of prompt data reporting, ASCO will only entertain DUA revisions related to the local site contact information.
- Contact [contact] to express interest in participation and execute DUA with ASCO.
- Access web address provided by ASCO for data entry and select practice name from the dropdown list of practices that have executed a DUA.
- Complete initial and follow-up data entry forms. Follow-up data includes information on COVID-19 and cancer treatment and outcomes. Ideally, data entry will be done routinely. ASCO requests case updates at 30-, 60-, 90-, 180-, 270-, and 360-day intervals, unless a patient has left the practice or died. Where necessary, practices should attempt to obtain information from inpatient hospitalizations.
 - Data includes:
 - Limited patient identifiable data, including home zip code, practice zip code, and date of birth
 - Demographics (e.g., gender, race, ethnicity, type of cancer, and comorbidities)
 - COVID-19 status (e.g. symptoms, treatments, and outcomes)
 - Cancer status (e.g., treatment plans, any changes to treatment plans, and response to treatments)
 - ASCO encourages practices to create a local standard operating procedure (SOP) to arrange systematic data entry. Retrospective data could be retrieved from the EHR using the new ICD-10-CM diagnosis code U07.1 (created by the Centers for Disease Control and Prevention (CDC) on March 18, 2020). Previous ICD-10-CM codes were 1)
 Coronavirus, as cause of disease classified elsewhere B97.29, 2) Coronavirus NEC B34.2, and 3) SARS-associated coronavirus J12.81. The coding system for laboratory and clinical test results (LOINC) has also established several codes for tests for the COVID-19 virus: SARS Coronavirus 2.
 - Practices may have to contact the hospital for information regarding an inpatient admission.
- ASCO provides participating sites with a practice-based stipend in the first 30 days following contract execution and case-based stipends after the first 30-day update to help cover the costs of entering registry data.

Participating practices are listed on the ASCO Registry webpage. Practices may withdraw from the registry at any time.

Please contact [contact] for additional information or questions.

The ASCO Registry is supported by Conquer Cancer's **COVID Impacts Cancer Fund**.

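### Does Objective 1 describe COVID-19 severity in a narrower group of patients than the registry enrols?

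*Protocol*

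**What the plan says.** Under Research Objectives, Objective 1 limits the description of symptoms and severity to "patients with cancer (on active treatment or on adjuvant treatment within 12 months after surgical resection". Objective 1.1 stratifies that description by patient characteristics, among them cancer extent and "type of therapy received, smoking status, comorbidities, etc". Objective 1.2 looks for correlates of severity and refers simply to cancer patients.

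The Eligibility Criteria say that registrants "are being treated at participating cancer practices/institutions within the United States" and list four categories:

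1. "Patients with a new cancer diagnosis and in the process of cancer staging and/or receipt of initial cancer therapy"
2. those already on therapy, worded as "Patients with clinically evident cancer receiving anti-cancer treatment"
3. disease-free patients "receiving any type of adjuvant therapy within 1 year following surgical resection"
4. those without such therapy, worded as "Patients with clinically evident cancer receiving supportive care only"

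The Project Objectives, which come before the Research Objectives, concern patients with cancer and COVID-19 without a treatment limit, and name symptom severity, ventilator need and hospitalization among the data. The Project Deliverables follow directly and promise "Periodic Reports on Patient Population, Estimates of Disease Severity, Treatment Modifications, and Clinical Outcomes Among Patients". Objective 2 covers infection and cancer outcomes, also without the limit. Statistical Considerations and Reporting plans overall and stratified summaries, with no hypothesis tests and no required sample size.

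**The concern.** Categories 2 and 3 match the two groups named in Objective 1 closely. Category 4 does not: the protocol itself separates supportive care from anti-cancer treatment. Category 1 matches only in part, because its wording admits patients who are in staging and have not started therapy. These patients are registered, yet Objective 1 read literally does not describe them.

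The reporting text does not repeat the limit. A reader cannot tell from the protocol whether an overall severity figure covers treated patients only or everyone registered. In a descriptive registry the population is a large part of what an estimate means, and these reports are to be public. If the two populations differ in severity, a figure for all registrants that was read as one for treated patients would mislead. A larger registry would not remove the difference, and the planned confidence intervals, which express precision, would not reveal it.

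**Working it through.** The protocol states no figure on this point, so there is none to reproduce. The check is a comparison of texts, followed by an illustration on assumed values.

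**Step 1. Which registrants does each statement cover?**

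| Eligibility category | Objective 1 | Project Objectives | Objective 2 |
|---|---|---|---|
| 1, therapy started | yes | yes | yes |
| 1, staging only | no | yes | yes |
| 2, anti-cancer treatment | yes | yes | yes |
| 3, adjuvant within 1 year | yes | yes | yes |
| 4, supportive care only | no | yes | yes |

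The two negative entries are the whole mismatch. Both groups have a place under the two unrestricted statements.

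**Step 2. Is severity covered for those two groups?** Yes. The Project Objectives name symptom severity, ventilator need and hospitalization. Objective 2 lists hospitalization outside and inside intensive care, ventilation and death from COVID-19. Objective 2.1 applies the Objective 1.1 characteristics, which include type of therapy and cancer extent, to patients with the infection generally. A separation by treatment is therefore planned for all registrants on these outcomes, even if Objective 1.1 is read as confined to the Objective 1 population.

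**Step 3. Do the reports contradict Objective 1?** No. The deliverables follow the Project Objectives, which are unrestricted, so a severity summary of all registrants agrees with them. In Statistical Considerations and Reporting, overall stands opposite stratified; it does not define an analysis set. The strata listed there are examples.

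**Step 4. Can the groups be told apart in the data?** Probably. The study calendar in the Appendix puts cancer diagnosis, status and treatment at initial entry. The entry form is not shown, so this is an assumption.

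**Step 5. How far could the two figures differ?** Let p be the severity proportion in the Objective 1 population, w the share of registrants outside it, and p + d the proportion among those registrants. Then

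all-registrant proportion = (1 - w)p + w(p + d) = p + wd,

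so the difference is w × d. The protocol gives neither w nor d. With assumed values, in percentage points:

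| w | d = -10 | d = 0 | d = +10 | d = +20 |
|---|---|---|---|---|
| 5% | -0.5 | 0 | +0.5 | +1.0 |
| 10% | -1.0 | 0 | +1.0 | +2.0 |
| 20% | -2.0 | 0 | +2.0 | +4.0 |

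The table leans upward only because the assumed range of d does; nothing in the protocol supports a direction. Each entry is the gap between two correctly defined quantities. It becomes an error only if one is published under the other's label.

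**The case for a change.** The best case for a change is that the document states two populations and never relates them. If Objective 1 is meant as a subset, one sentence could say so. Instead Objective 1.2 and the reporting text drop the limit, and whoever writes the analysis plan must choose. Type of therapy as a stratifier helps the stratified tables but does not define the overall row. Describing severity is the first research objective of a registry with no hypothesis test, and clarifying the wording would cost almost nothing.

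Much of this stands. The wording is loose, the subset status is unstated, and the stratifier does not fix the overall denominator. What does not follow is a wrong result. Either reading gives a valid descriptive estimate, and choosing which registrants enter which table is ordinary analysis-set work that a protocol may leave to a later plan. The harm depends on mislabelled reports, which the protocol does not foreshadow; the patient population is itself a listed report topic.

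A mandatory severity table by eligibility category would add little. It would largely repeat the stratification by therapy, and if Objective 1 were confined to treated patients, it would have no Objective 1 estimates for category 4 or for patients in staging only.

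The Rationale's phrase about patients undergoing treatment adds little weight. It is a one-line introduction, and the eligibility lead-in describes every registrant as treated at a participating practice.

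**Conclusion.** The mismatch is confirmed but minor, and no change to the plan follows. Objective 1 leaves out category 4 and the staging-only part of category 1; the Project Objectives and Objective 2 cover both. This is a gap in wording that analysts fill when they define and label the denominator of each severity summary.

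The size cannot be determined from the protocol. The span of -2.0 to +4.0 points rests wholly on assumed shares and differences, and it is zero if severity does not differ between the groups. No error rate, power or sample size is involved.

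The conclusion assumes that the initial entry data identify treatment status and that reports say whom each figure covers. A report that gave an all-registrant figure as one for treated patients would be a fault of that report; following the protocol does not produce it.

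### The only fatal SARS-CoV-2 outcome is cause-attributed with no time window, so comparing it by cancer extent and therapy is open to attribution error; report all-cause death by day 30 and day 90 beside it

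*Protocol*

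**What the plan says.** Objective 2 (Research Objectives) sets out two outcome lists. The SARS-CoV-2 list runs from ongoing infection to death, and its only fatal entry is "death due to COVID-19 disease complications". The second list is "cancer outcomes (stable, response to treatment, progression, delayed treatment, treatment discontinued, and death"; its death entry carries no cause. Neither list gives a time window.

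Objective 2.1 is to "Stratify patients with SARS-CoV-2 viral infection according to characteristics" from Objective 1.1 and to examine whether any of them are independently "associated with COVID-19 and/or cancer outcomes". The Objective 1.1 characteristics are "age, cancer type, cancer extent, race, ethnicity, geography, type of therapy received, smoking status, comorbidities, etc".

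Eligibility Criteria admit four groups. At one end are disease-free patients on adjuvant therapy within a year of resection. At the other are "Patients with clinically evident cancer receiving supportive care only".

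Under Practice Expectations, the practice's task is to "Complete initial and follow-up data entry forms. Follow-up data includes information on COVID-19 and cancer treatment and outcomes". Updates are requested at 30, 60, 90, 180, 270 and 360 days unless the patient has died or left the practice. Practices are asked to try to obtain inpatient information where necessary. The protocol shows no rule for attributing a death to COVID-19 and no adjudication. The data collection forms are not part of the document.

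**The concern.** To record the fatal SARS-CoV-2 outcome, someone must judge whether the infection or the cancer caused the death. In a disease-free adjuvant patient, cancer will seldom be a rival explanation for an early death. In a supportive-care patient it usually will be. The difficulty of the judgement therefore tracks cancer extent and therapy, which are two of the factors that Objective 2.1 compares.

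If the error rates differ along those factors, the association between cancer extent (or therapy) and COVID-19 death can be created, hidden or exaggerated. Covariate adjustment does not remove an outcome error that depends on the exposure. Nor do the confidence intervals promised under Statistical Considerations and Reporting reflect it. The absence of hypothesis tests is no protection, because it is the estimates themselves that are affected. They are meant for public reports and manuscripts.

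**Working it through.** The protocol states no fatality rate, event count or sample size, so there is no figure to reproduce. Every input below is an assumption, used only to show the possible direction and size.

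**Formula.** Observed attributed fatality = (true COVID-19 fatality × sensitivity of attribution) + (other-cause death × proportion falsely attributed). The risk ratio (RR) is advanced over localised disease.

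**Set A: no true difference.** True COVID-19 fatality is 15% in both groups (true RR 1.00). Other-cause death (localised, advanced) is either 1% and 5% or 2% and 12%.

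| Attribution (localised, advanced) | RR at 1% and 5% | RR at 2% and 12% |
|---|---|---|
| Perfect | 1.00 | 1.00 |
| Same errors: sensitivity 95%, false attribution 10% | 0.1475/0.1435 = 1.03 | 0.1545/0.1445 = 1.07 |
| Sensitivity 95%, 70%; false attribution 5% in both | 0.1075/0.1430 = 0.75 | 0.1110/0.1435 = 0.77 |
| Sensitivity 95% in both; false attribution 5%, 40% | 0.1625/0.1430 = 1.14 | 0.1905/0.1435 = 1.33 |
| Sensitivity 95%, 80%; false attribution 5%, 30% | 0.1350/0.1430 = 0.94 | 0.1560/0.1435 = 1.09 |
| All-cause death | 0.20/0.16 = 1.25 | 0.27/0.17 = 1.59 |

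**Set B: a true difference.** True COVID-19 fatality is 10% in localised and 20% in advanced disease (true RR 2.0). Other-cause death is 1% and 10%.

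- Under-attribution only, sensitivity 95% in localised and s in advanced disease: 0.20s/(0.10 × 0.95). For s = 60%, 70%, 80% and 90%, RR = 1.26, 1.47, 1.68 and 1.89.
- Over-attribution only, with the same share m of other-cause deaths mislabelled in both groups: (0.20 + 0.10m)/(0.10 + 0.01m). For m = 10% to 30%, RR = 2.08 to 2.23.
- Both errors, m = 20%: with s = 90%, (0.18 + 0.02)/(0.095 + 0.002) = 2.06; with s = 80%, (0.16 + 0.02)/0.097 = 1.86.
- All-cause death: (0.20 + 0.10)/(0.10 + 0.01) = 2.73.

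**Reading.** The attributed RR can move either way, and the two errors can nearly cancel. All-cause death has no attribution error, but it lies above the true COVID-19 RR because other-cause deaths also rise with cancer extent. It departs further as background mortality grows, as it would with a longer window. Neither measure is sufficient alone.

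**The case against.** The strongest reply has four parts.

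1. **Nothing in the protocol shows that attribution differs by cancer extent or therapy.** This stands. A reader might infer that the Objective 2.1 fatality comparisons are biased. The document supports only that they are open to bias, and offsetting errors can leave little.

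2. **Death without a cause is already in the cancer list, and Objective 2.1 covers that list too.** This stands in part. If the item means any death, an all-cause comparison is already in scope. But the protocol does not say whether it means any death or cancer death, and it fixes no window from COVID-19 diagnosis for it.

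3. **Attribution rules and analysis windows may sit in the forms or a statistical analysis plan, neither of which is shown.** This stands as far as the absence of a rule goes, and that absence is not the point made here. That the practice judges the cause is likewise inferred from its completing the forms. What remains is that the protocol itself, in Objective 2, makes an attributed cause the only route to a fatal SARS-CoV-2 outcome.

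4. **All-cause death is a different estimand and not plainly better.** This stands. On Set B it gives 2.73 against a true 2.0, further off than any of the over-attribution figures. Interest in infection outcomes makes cause-specific death a legitimate choice. A reader might conclude that all-cause death should replace the attributed outcome or rank above it; the documents and the arithmetic do not support that.

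**Conclusion.** The point holds as a vulnerability in how Objective 2 defines its fatal SARS-CoV-2 outcome, not as a demonstrated bias. That outcome rests on attribution alone and has no window, while Objective 2.1 compares it across groups whose competing risk of cancer death differs widely. Direction and size are unknown. On the assumed inputs, a true RR of 1.00 could appear as anything from 0.75 to 1.33, and a true RR of 2.0 as anything from 1.26 to 2.23; in both sets some combinations of errors land close to the truth. The illustration contrasts localised with advanced disease; for therapy the argument is the same but no figures were worked. This is a cheap improvement that would let a reader see whether a gradient by extent or therapy depends on attribution.

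**What to change.** In Objective 2:

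- Add death from any cause by day 30 and by day 90 from COVID-19 diagnosis as a fatal outcome reported beside "death due to COVID-19 disease complications", neither replacing nor demoting it.
- Show both measures by cancer extent and by therapy.
- State that death in the cancer list means death from any cause, or name it otherwise.

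**Cost.** A wording change and an extra line per table. Days 30 and 90 are already scheduled update points. Date of death is not among the data named under Practice Expectations, so confirm that the forms capture it, or at least vital status at the 30- and 90-day updates.

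**Downside.** All-cause death includes background cancer deaths that rise with cancer extent, more so by day 90 than by day 30. The reports should say that the two measures are to be read together.

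### Does the protocol go too far in saying that repeated cumulative reports leave its results valid, given that Objectives 1.2, 2.1 and 2.2 look for independent associations?

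*Protocol*

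**What the plan says.** The statement is in the protocol, Statistical Considerations and Reporting, and gives this reasoning: "no hypothesis testing planned, there is no required sample size and providing repeated reports, with cumulative information, will not affect validity of results". The next sentence provides for confidence intervals, where suitable, to show how precise the estimates are.

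The same section describes the periodic reports as summaries, overall and by patient characteristics, together with treatment delay and discontinuation and changes in practice patterns. It names manuscripts as a separate output. Project Deliverables makes the same division: "Periodic Reports on Patient Population, Estimates of Disease Severity, Treatment Modifications, and Clinical Outcomes Among Patients" is one item and "Manuscript(s) for Submission to Peer-Reviewed Journals" is another. The Project Objectives open descriptively: "Capture and describe cancer and COVID-19 status at COVID-19 diagnosis".

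Three research objectives go beyond description:

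- Objective 1.2: "Identify characteristics independently associated with severity of COVID-19 in cancer patients".
- Objective 2.1: stratify patients "to examine whether any of the characteristics are independently" associated with COVID-19 or cancer outcomes.
- Objective 2.2: "whether SARS-CoV-2 viral infection outcomes are independently associated with cancer outcomes".

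The protocol gives no number or dates of reports, no confidence level, no rule for declaring an association, and no statement that association models will be refitted at each report.

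**The concern.** The sentence speaks of results in general and is not limited to descriptive ones. Its reason is that nothing is tested. Yet identifying characteristics, or asking whether an association exists, calls for a selection or a yes/no answer, and leaving out the word test does not protect an estimate that was picked because of what one data cut showed. Manuscripts are not tied to a cut, reports are public, and the Rationale wants practices to "rapidly submit data that will inform both current cancer care".

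If associations were picked from whichever cut first showed them, there would be too many false ones, their intervals would cover too rarely, and the estimates would be exaggerated. The protocol's assurance would then appear to vouch for them.

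**Working it through.** **Inputs.** The protocol states no sample size, error rate, power or number of reports, so it has no figure to reproduce. Everything numerical here is assumed: two-sided 95% intervals (critical value 1.96), K cumulative cuts, equal spacing unless stated, and one association that is truly null.

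**Model.** Let X₁, …, X_K be independent standard normal increments. At cut k the statistic is Z_k = (X₁ + … + X_k)/√k. Each Z_k is standard normal, and corr(Z_j, Z_k) = √(j/k) for j ≤ k.

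**Step 1: each report taken alone.** P(|Z_k| > 1.96) = 0.05 at every k, however many reports came before. In simulation (1,000,000 draws) the error at single reports was 0.0496 to 0.0503. Each interval therefore keeps its 95% coverage. This is the situation the sentence describes, and there it is true.

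**Step 2: an added rule.** Now suppose an association is declared if the interval excludes no effect at any cut. The false-declaration rate is P(max over k of |Z_k| > 1.96):

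| K | Declared at some cut | Declared, but not at the last cut | Share lost by the last cut |
|---|---|---|---|
| 1 | 0.0500 | – | – |
| 2 | 0.0831 | 0.0831 − 0.0500 = 0.0331 | 0.0331/0.0831 = 39.8% |
| 4 | 0.1262 | 0.1262 − 0.0500 = 0.0762 | 0.0762/0.1262 = 60.4% |
| 10 | 0.1934 | 0.1934 − 0.0500 = 0.1434 | 0.1434/0.1934 = 74.1% |

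In the unequal timings examined, the rate runs from 0.0648 to 0.0949 (K = 2), 0.0900 to 0.1545 (K = 4) and 0.1146 to 0.2258 (K = 10).

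**Step 3: estimates under the same rule.** If the first cut that excludes no effect is reported, and otherwise the last, coverage for a null effect falls from 95.0% to 87.3% (K = 4) or 84.5% (K = 6). For a weak true effect (expected z of 1.0 at the last cut), the selected estimates average 3.04 times the truth at K = 4.

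**Step 4: does the protocol contain the rule?** Steps 2 and 3 need three things: association models run at successive cuts, a declaration whenever an interval excludes no effect, and retention of the earliest positive result. The protocol states none of them. It gives the reports a summary content, gives the intervals the purpose of showing precision, and lists manuscripts separately. Because the reports are cumulative, each one naturally supersedes the last, and the error at the latest report is then 5.0% (step 1).

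**Step 5: do the reports harm a later association analysis?** An adjusted estimate at a given cut depends only on the data at that cut. Having published earlier summaries does not alter it. The protocol has no rule that closes the registry because of a result, so the reports do not act as stopping looks either. If the cut for Objectives 1.2, 2.1 and 2.2 is chosen without regard to its results, the error stays at 5.0% per association.

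**The case for a change.** The strongest reply is that this is a positive statement and not an omission. It is worded without limit, and an unlimited assurance is wrong if it fails in any use the document leaves open. Association analyses are planned, several manuscripts may appear, and none is tied to a cut. Step 3 also shows that estimates and intervals suffer, not just tests, so the absence of testing would be no defence under that rule.

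Part of this stands. The wording carries no written restriction, the three objectives do go beyond description, and selecting across cuts would do the damage calculated. Each interval is also valid report by report only, not jointly over all reports.

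What does not stand is the step from possible to planned. The sentence is about providing reports, and it has to be read with the protocol's own account of what those reports contain. The failure comes from a selection rule that a reader must add, and that rule is itself a form of testing in a plan that says it does none. Choosing the cut, the assessment time and any multiplicity procedure for the association models is commonly left to a statistical analysis plan, which may exist here. Labelling the associations exploratory would not separate a cut named in advance from any other unless that plan sets such a procedure, since both would carry the same label.

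**Conclusion.** The concern does not hold. For the cumulative summaries the protocol describes, the statement is correct: every report keeps its nominal 95% coverage. Issuing those summaries also leaves a later analysis of Objectives 1.2, 2.1 and 2.2 unaffected, with 5.0% error per null association at a cut chosen without regard to its results. The rise to 8.3%, 12.6% or 19.3% (2, 4 or 10 equally spaced cuts) is sound arithmetic for a rule the protocol does not contain.

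This conclusion rests on two readings: that the reports are the summaries the protocol says they are, and that associations are not declared from whichever cut first shows them. If a statistical analysis plan or a manuscript did declare them that way, the problem would lie in that document and should be raised there. Limiting the sentence explicitly to descriptive estimates would be a harmless clarification, but it is a preference about wording and changes no result the plan would produce.
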